4.1.4 Enrollment procedures

Subjects deriving clinical benefit (CR / PR / SD) with platinum-based therapy will be randomized to each of the treatment arms (olaparib or olaparib in combination with durvalumab) through the use of a stratified permuted block randomization in a 1:1 ratio to ensure within-stratum balance of characteristics between treatment arms. The stratification will be based on line of chemotherapy and by site. Randomization will be used to allocate subjects to either the olaparib or olaparib in combination with the durvalumab arm, and comparisons between treatment regimens are planned. The purpose of randomization is to reduce bias due to subject selection into either treatment arm.

There are five institutions participating as study sites in three countries including USA, Singapore, and South Korea. Each site will complete an eligibility checklist and enrollment must be submitted and approved prior to the randomization of any subject. The details of this procedure is provided in the site initiation materials.

4.1.5 Post-platinum chemotherapy tumor evaluation

Initial tumor assessment to assess for response to platinum chemotherapy will be performed as per standard of care following at least three 3-weekly (q21 day) or six 1-weekly doses of platinum chemotherapy. Attempts should be made to minimize time off treatment to less than 3 weeks. Any measurable disease must be documented at screening and re-assessed at tumor evaluation. Measurable disease is not required to go on study. Response assessments will be performed by the Investigator on the basis of physical examinations and imaging scans. Eligibility requires stable disease (SD), partial response (PR) or complete response (CR) per investigator assessment to the platinum therapy.

The same imaging method used at screening/baseline must be maintained throughout the study.

Computerized tomography (CT) scans are the preferred imaging modality for tumor assessments. Tumor assessments should include a diagnostic quality contrast-enhanced CT scan of the chest, abdomen, and pelvis at baseline. Computerized tomography (CT) scans of the neck should be included if there is clinical indication. Subsequent tumor assessments should include CT scans of the chest, abdomen, pelvis, and other known sites of disease. In addition to the

scheduled protocol scans, CT scans may be performed at the Investigator's discretion at any time if progressive disease is suspected.

In subjects for whom a CT scan is contraindicated because of an allergy to IV radiographic contrast, both CT scan of the chest without contrast and a magnetic resonance imaging (MRI) scan with contrast of the abdomen and pelvis and neck if clinically indicated are recommended; MRI scans may be performed in lieu of CT scans. Subsequent tumor assessments should include MRI scans of the chest, abdomen, pelvis, and other known sites of disease. The CT or MRI scans may be repeated at the Investigator's discretion at any time if progressive disease is suspected.

At the Investigator's discretion and if clinically indicated, other methods of assessment of measurable disease per RECIST 1.1 may be used (eg, brain scans using CT or MRI) in addition to those listed above. Additional procedures for tumor assessment should be performed as clinically indicated.

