3.4 Inclusion Criteria

Subjects must meet all of the below criteria to be eligible for randomization and study treatment.

1. Age \geq 21 years of age
2. ECOG performance status 0-2
3. Inoperable locally advanced or metastatic breast cancer not amenable to resection with curative intent and histologically confirmed to be estrogen receptor (ER) negative, progesterone receptor (PR) negative, and HER2 negative:
 - ER negative status is defined as $< 1\%$ tumor cells positive for ER by immunohistochemistry (IHC), irrespective of staining intensity
 - PR negative status is defined as $< 1\%$ tumor cells positive for PR by IHC, irrespective of staining intensity
 - NOTE: Enrollment is permitted for ER/PR low-expression subjects (defined as $\leq 10\%$) who are expected to benefit from this trial at the investigator's discretion.
 - HER2 negative status is determined by:
 - IHC 1+, as defined by incomplete membrane staining that is faint/barely perceptible and within $> 10\%$ of invasive tumor cells, or
 - IHC 0, as defined by no staining observed or membrane staining that is incomplete and is faint/barely perceptible and within $\leq 10\%$ of the invasive tumor cells, or
 - FISH negative based on:
 - Single-probe average HER2 copy number < 4.0 signals / cell, or
 - Dual-probe HER2/CEP17 ratio < 2.0 with an average HER2 copy number < 4.0 signals / cell

4. Minimum six 1-weekly doses or three 3-weekly doses of platinum chemotherapy (monotherapy or combination therapy at investigator's discretion) with stable disease (SD), partial response (PR) or complete response (CR) to the platinum therapy as assessed by investigator.
5. Has received no more than 2 prior chemotherapy lines for metastatic breast cancer including current platinum-based chemotherapy.
6. Able to provide a representative formalin-fixed, paraffin embedded tumor specimen archival or fresh tissue for correlative studies and biomarker analysis.
7. Hemoglobin ≥ 9.0 g/dL and no blood transfusions in the 28 days prior to study entry. Absolute neutrophil count $\geq 1,500/\text{mm}^3$. Platelet count $\geq 100 \times 10^9/\text{L}$.
8. Total bilirubin $< 1.5 \times$ the upper limit of normal (ULN) with the following exception: subjects with known Gilbert's disease who have serum bilirubin $< 3 \times$ ULN may be enrolled.

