3.8 Evaluation and calculation of variables

The primary efficacy outcome measure is as follows:

- PFS (progression free survival) defined as the time from randomization to the first occurrence of disease progression (as determined using RECIST 1.1 criteria and assessed by the Investigator) or death from any cause on study. Death on study is defined as death from any cause within 30 days of the last dose of study treatment regimen. Tumor progression will be assessed locally at each site by the investigators according to RECIST 1.1. No independent review of tumor progression is planned. PFS with disease progression determined by iRECIST for patients on the combination arm will also be examined in exploratory data analysis.

The secondary efficacy outcome measures in all subjects are as follows:

- OS (overall survival) defined as the time from entry onto trial until death from any cause.
- ORR (overall response rate) defined as the subjects achieving Complete Response or Partial Response as defined by RECIST 1.1.
- CBR (clinical benefit rate) defined as subjects achieving Complete Response, Partial Response or Stable disease \geq 24 weeks

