4.1.3 Baseline documentation of “target” and “non-target” lesions

All measurable lesions (nodal and non-nodal) up to a maximum of five lesions in total (and a maximum of 2 lesions per organ), representative of all involved organs, should be identified as **target lesions** and recorded and measured at baseline. Target lesions must be 10 mm in the longest diameter to qualify, or 15 mm in the short diameter for lymph nodes. Target lesions should be selected on the basis of their size (lesions with the longest diameter) and their suitability for accurate repeated measurements (either by imaging techniques or clinical assessments).

A sum of the longest diameter (LD) for *all target lesions* will be calculated and reported as the baseline sum LD. The baseline sum LD will be used as the reference by which to characterize the objective tumor response.

All other lesions (or sites of disease) should be identified as **non-target lesions** and should also be recorded at baseline. Measurements of these lesions are not required, but the presence or absence of each should be noted throughout follow-up.

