4.8.1 Efficacy outcome measures

Only response evaluation per RECIST will be entered into eCRF for the Extension period.

The primary efficacy outcome measure is as follows:

PFS, defined as the time from randomization to the first occurrence of disease progression (as determined using RECIST v1.1 criteria and assessed by the Investigator) or death from any cause on study. Death on study is defined as death from any cause within 30 days of the last dose of study treatment regimen. Tumor progression will be assessed locally at each site by the investigators according to RECIST 1.1. No independent review of tumor progression is planned. PFS with disease progression determined by iRECIST will also be examined in exploratory data analysis for the combination arm. The secondary efficacy outcome measures in all subjects are as follows:

- OS (overall survival) defined as the time from randomization until death from any cause.

- ORR (overall response rate) defined as the subjects achieving Complete Response or Partial Response as defined by RECIST 1.1.
- CBR (clinical benefit rate) defined as subjects achieving Complete Response, Partial Response or Stable disease \geq 24 weeks

Methods of measurement

The following definitions and criteria (from RECIST 1.1) should be used for the baseline evaluations of existing disease and for the ongoing evaluation of tumor responses. All measurements should be taken and recorded in metric notation, using a ruler or callipers. In the case of skin lesions, documentation by color photography and a measurement with a ruler to estimate the size of the lesion is recommended.

- **Measurable disease** - the presence of at least one measurable lesion.
- **Measurable lesions** – non-lymph node lesions that can be accurately measured in at least one dimension with LD 20 mm using conventional techniques or 10 mm with spiral CT scan, or 15mm for lymph nodes with spiral CT.
- **Non-measurable lesions** - all other lesions ie, bone lesions, ascites, pleural/pericardial effusion, including lesions that do not meet the measureable criteria above.
- Conventional CT should be performed with cuts of 10 mm or less in slice thickness contiguously. Spiral CT should be performed using a 5-mm contiguous reconstruction algorithm.

All imaging methods should be performed according to institutional standards with each subject having consistency of methods beginning from baseline through the course of the study.

Table 9: Response criteria

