Evaluation of target lesions	
Complete Response (CR):	Disappearance of all target lesions
Partial Response (PR):	At least 30% decrease in the sum of the LD of target lesions, taking as reference the baseline sum LD
Progressive Disease (PD):	At least a 20% increase in the sum of the LD of target lesions, taking as reference the nadir (smallest sum) LD recorded since the treatment started or the appearance of one or more new lesions
Stable Disease (SD)	Neither sufficient shrinkage to qualify for PR nor sufficient increase to qualify for PD, taking as reference the smallest sum LD since the treatment started
Evaluation of non-target lesions	
Complete Response (CR):	Disappearance of all target lesions
Stable Disease (SD)	Persistence of one or more non-target lesion(s)

Progressive Disease (PD):	Appearance of one or more new lesions and/or unequivocal progression of existing non-target lesions
---------------------------	---

Evaluation of Best Overall Response

The best overall response is the best response recorded from the start of the treatment until disease progression and is determined as per Table 10 below.

Table 10: Definition of best overall response as per RECIST criteria

Target lesions	Non-Target lesions	Evaluation of New lesions	Overall response
CR	CR	No	CR
CR	SD	No	PR
PR	Non-PD	No	PR
SD	Non-PD	No	SD
PD	Any	Yes or No	PD
Any	PD	Yes or No	PD
Any	Any	Yes	PD

To be considered a response, CR or PR must persist for a minimum of 4 weeks. If, at the time of tumor response evaluation, either a PR or CR is observed, the same radiographic study should be repeated 4 weeks later for confirmation of response. After this confirmatory study, subjects should return to the schedule of evaluations as previously described.

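### ORR and CBR are listed for all subjects, but subjects without target lesions cannot have a PR, Table 10 gives them no category except PD, and Table 9 misdefines non-target CR

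*Combined protocol and SAP*

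**What the plan says.** **Entry.** Protocol section 4.1.5: "Measurable disease is not required to go on study". Inclusion criterion 4 (section 3.4) admits subjects "with stable disease (SD), partial response (PR) or complete response (CR) to the platinum therapy as assessed by investigator". Two kinds of subject can therefore start maintenance without a target lesion: those with only non-target disease, and those with no visible disease left.

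**Endpoints.** Section 3.8 introduces ORR and CBR with "The secondary efficacy outcome measures in all subjects are as follows", and section 4.8.1 does the same. The definitions are "ORR (overall response rate) defined as the subjects achieving Complete Response or Partial Response as defined by RECIST 1.1" and "CBR (clinical benefit rate) defined as subjects achieving Complete Response, Partial Response or Stable disease", the stable disease lasting at least 24 weeks. Section 7.1 gives no analysis set, target rate or handling rule for either endpoint.

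**Response rules.** Section 4.1.3 makes the measurable lesions the target lesions and adds: "The baseline sum LD will be used as the reference by which to characterize the objective tumor response". Table 9 (section 4.8.1) defines PR for target lesions only: "At least 30% decrease in the sum of the LD of target lesions, taking as reference the baseline sum LD". For non-target lesions it gives CR, SD and PD. Its CR text there is the same as for target lesions; it does not mention non-target lesions at all. Section 4.8.1 then takes best overall response from Table 10, counted from the start of treatment.

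**The concern.** The eligibility rule and the response rules do not fit together. The trial admits subjects for whom the printed response tables have no place, and then counts all subjects in ORR and CBR.

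Two things are at stake. First, the ORR denominator includes subjects who cannot have a PR, so the estimate is not a shrinkage rate among those who could show shrinkage. Second, the protocol does not say how a stable non-target-only subject, a non-target CR on treatment, or a subject still free of disease after an entry CR is to be scored. Investigators assess response locally, so two sites could score the same course differently. With about 30 subjects per arm, a few such decisions are visible in the result.

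ORR and CBR are secondary objectives in each arm (section 2.2). They carry no hypothesis or power statement.

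**Working it through.** The documents state no ORR figure, so there is none to reproduce. The check has two parts.

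**1. Table 10 for a subject with no target lesion at baseline**

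Each of the seven rows was compared with each possible status. The three rows for CR or PR need a target status of CR or PR, and the SD row needs target SD. Only PD rows accept any target status.

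| Non-target status | New lesion | Overall response from Table 10 |
|---|---|---|
| CR | No | no row fits |
| SD | No | no row fits |
| No non-target lesions (entry CR) | No | no row fits |
| PD | No | PD |
| Any | Yes | PD |

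So PD is the only response the table can assign. This is also why PFS is not blocked: non-target progression and new lesions still map to PD.

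**2. Illustration of size**

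From section 7.1: 30 subjects per arm. Assumed, because the documents give no counts: 6 of the 30 have no target lesion, and 5 of the other 24 respond. Intervals are exact (Clopper-Pearson): the lower limit is the 2.5th percentile of Beta(x, n−x+1), the upper limit the 97.5th percentile of Beta(x+1, n−x).

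| Analysis | ORR | 95% CI |
|---|---|---|
| Measurable disease | 5/24 = 20.8% | 7.1 to 42.2 |
| All subjects, none of the six responds | 5/30 = 16.7% | 5.6 to 34.7 |
| All subjects, one confirmed non-target CR accepted as CR | 6/30 = 20.0% | 7.7 to 38.6 |
| All subjects, two such CRs | 7/30 = 23.3% | 9.9 to 42.3 |

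The gap between the first two rows is 20.8 − 16.7 = 4.1 points. The all-subject figure equals the measurable-disease figure when (5 + k)/30 = 5/24, that is k = 30 × 5/24 − 5 = 1.25. With two or more non-target CRs the all-subject ORR is the higher one, so the direction of the difference is not fixed either.

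The share without target lesions is the main unknown. If the response rate in measurable disease is r, a fraction f has no target lesion and none of those responds, the expected all-subject ORR is r(1 − f):

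| f | 0% | 10% | 20% | 30% | 40% | 50% |
|---|---|---|---|---|---|---|
| r = 20% (assumed) | 20% | 18% | 16% | 14% | 12% | 10% |
| r = 30% (assumed) | 30% | 27% | 24% | 21% | 18% | 15% |

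**The case against.** The best defence has four parts.

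- **RECIST 1.1 governs.** ORR is defined by reference to that standard, which may cover non-target-only disease. This cannot be checked from the documents, so it would be wrong to say that no governing rule exists. But section 4.8.1 tells sites to use the printed criteria and Table 10, and these are incomplete. Section 3.9.1 also cites a Table 11 that does not appear in the text. This is probably stale numbering, since section 4.6.1 likewise cites Table 9 for blood volumes that stand in Table 8. If a Table 11 for these subjects exists, restoring it is part of the same correction.
- **An all-subject ORR is legitimate and conservative.** This stands. It is the planned analysis and should stay.
- **The trial is at its Extension stage, is open-label, and has a committee that reviews progression about every two months during accrual (section 7.2).** Replacing the main ORR set now could look like a choice made after seeing data. This stands too, and the fix below respects it.
- **Nothing primary is touched.** Agreed.

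Two stronger conclusions are tempting. A reader might infer that subjects without target lesions can never be responders and can never count towards CBR. The documents do not force this: Table 9 has separate CR and SD categories for non-target lesions, and the natural reading of its CR entry is a slip. On that reading non-target-only subjects can score CR or SD, and only a Table 10 line is missing.

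A reader might also infer that having no target lesions satisfies the target CR rule, so that stable non-target disease becomes a PR through the row for target CR with non-target SD. In the illustration this could lift ORR as far as (5 + 6)/30 = 36.7%. The text points against it: the reference is the baseline target sum, PR needs a 30% fall in that sum, and best response counts from the start of treatment. No effect size should be built on that reading.

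**Conclusion.** The point holds as a gap in the definitions of two secondary endpoints plus one wrong table entry. Three facts rest on the text alone: subjects without target lesions are eligible and counted; they cannot have a PR; and Table 10 offers them only PD. The Table 9 entry for non-target CR is wrong whatever view is taken of the rest.

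How much this moves ORR or CBR is unknown. The 4.1-point difference is an illustration that rests on an assumed 5 responders, an assumed 6 subjects without target lesions, and no response among those six. The two intervals overlap heavily. The documents do not support a claim that ORR is necessarily diluted or inflated. PFS and the sample size are unaffected.

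**What to change.** 1. **Table 9.** Make non-target CR mean that all non-target lesions have disappeared.
2. **Table 10.** Add rows for subjects with no target lesions:
   - non-target CR gives CR;
   - non-CR/non-PD stays non-CR/non-PD, not PR;
   - non-target PD or a new lesion gives PD;
   - no disease at baseline and no new lesion gives no evidence of disease, which is not a response.
3. **CBR.** Count non-CR/non-PD and entry-CR subjects only if they are progression-free for at least 24 weeks.
4. **ORR.** Keep the planned all-subject ORR. Beside it, report ORR in subjects with measurable disease at the post-platinum baseline, with the number of non-target-only and entry-CR subjects in each arm. If data have already been reviewed, label this analysis as added by amendment.

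**Cost.** One table entry, four table rows and some definition wording. Baseline lesion records show who has no target lesion, and for non-target lesions section 4.1.3 already asks that "the presence or absence of each should be noted throughout follow-up". In the Extension period only the RECIST response evaluation enters the eCRF (section 4.8.1), so some non-target status may have to be retrieved from source records. The measurable-disease analysis has a smaller denominator and a wider interval: 42.2 − 7.1 = 35.1 points for 5/24, against 34.7 − 5.6 = 29.1 points for 5/30 in the illustration.

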4.1.6 Procedures for randomization

Subjects with CR, PR, or SD by investigator assessment following minimum requirements in inclusion criteria of platinum-based chemotherapy are eligible to consent and complete screening activities. Subjects who meet all eligibility requirements will be randomly allocated to each of the treatment arms (olaparib or olaparib in combination with durvalumab).

Subjects will be allocated to each of the treatment arms (olaparib or olaparib in combination with durvalumab) through the use of a stratified permuted block randomization in a 1:1 ratio, to ensure within-stratum balance of characteristics between treatment arms. Randomization will be stratified by line of chemotherapy (1st vs 2nd) and by site.

4.1.7 Procedures for handling ineligible or screen-fail subjects

Subjects who signed the study informed consent form but are considered ineligible after screening will be considered as screening failures, and data will be handled as follows: The demographic information, informed consent, and inclusion/exclusion criteria will be collected for screen failure subjects. No other data will be collected for subjects who are screen failures unless the subject experienced a serious adverse event during the screening phase that is possibly related to a study procedure.

4.2 Treatments

Subjects will continue on study drug(s) until objective disease progression, as long as in the Investigator's opinion they are benefiting from treatment and they do not meet any other discontinuation criteria.

4.2.1 Identity of investigational product(s)

The AstraZeneca Pharmaceutical Development R&D Supply Chain will supply olaparib and the durvalumab to the Investigator/sponsor's dispensing vendor. This vendor will distribute drug supply to the participating sites.

Table 2: Identity of Investigational Product

Investigational product	Dosage form and strength
Olaparib	150 mg oral tablet and 100mg oral tablet (100mg for dose reductions only)
Durvalumab	1500 mg intravenous

^a Descriptive information for olaparib can be found in the Investigator's Brochure

4.2.2 Olaparib

Olaparib (AZD 2281) (as film-coated tablet formulation) is intended for oral administration. The tablet monotherapy dose and the dose that will be used in this study is 300 mg bid taken continuously in 28 day cycles.

4.2.3 Olaparib: doses and treatment regimens

For all centers, olaparib tablets will be packed in high-density polyethylene (HDPE) bottles with child-resistant closures. Each dosing container will contain 32 tablets and desiccant. Multiple bottles of study treatment may be required for dispensing in order to make up the desired dose.

Olaparib will be dispensed to subjects on Day 1 and approximately every 28 days thereafter until the subject completes the study, the subject withdraws from the study or closure of the study.

The olaparib tablets should be swallowed whole and not chewed, crushed, dissolved, or divided.

The effect of food on olaparib tablet has been investigated. Co-administration with food slowed the rate of absorption (t_{max} delayed by 2.5 hours and C_{max} reduced by 20%), however food did not significantly affect AUC, therefore olaparib tablet formulation can be given without regard to food.

If vomiting occurs shortly after the olaparib tablets are swallowed, the dose should only be replaced if all of the intact tablets can be seen and counted. Should any subject enrolled on the study miss a scheduled dose for whatever reason (eg, as a result of forgetting to take the tablets or vomiting), the subject will be allowed to take the scheduled dose up to a maximum of 2 hours after that scheduled dose time. If longer than 2 hours after the scheduled dose time, the missed dose is not to be taken and the subject should take their allotted dose at the next scheduled time.

Subjects will continue with olaparib until objective disease progression (determined by RECIST) as long as in the Investigator's opinion they are benefiting from treatment and they do not meet any other discontinuation criteria.

